14.4. Type I error rate

The Type I error rate is 5% and all tests are two-tailed.

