14.5.4. Power

The assumptions underlying the power analysis for MET-weighted minutes of MVPA are summarized in Table 14.1.

- The mean and standard deviation for MET-weighted minutes of MVPA are taken from the variance components substudy of 8th grade girls (n=426) selected to represent 12 schools from the six Field Centers. Both are based on a cutpoint of 1500 CSA counts per half-minute to define MVPA, a figure drawn from the findings of the CSA calibration substudy.
- As noted above, the Type I error rate for the primary analysis is 5% and twotailed.
- Given 60 girls per school invited to the baseline survey, we conservatively
 estimate the overtime correlation among schools at zero (the correlation among
 measures taken on the same schools two years apart). We make no provision
 for overtime correlation among the girls (the correlation among measures taken
 on the same girls two years apart), due to our plan to ignore any overlap in the
 6th and 8th grade samples.
- We plan to randomize 18 schools to each of two conditions.
- We assume each Field Center will average 60 girls per school selected for invitation to the baseline survey and 120 girls per school selected for invitation to the follow-up survey. Schools with fewer girls available for CSA measurements may participate in TAAG so long as there is a minimum of 90 girls who are eligible to be selected for invitation to each survey and so long as each Field Center averages 60 girls per school at the baseline survey and 120 girls per school at the follow-up survey.
- We anticipate that girls enrolled in the intervention schools during 7th and 8th grade will display an intervention effect of 15.6 more MET-weighted minutes of MVPA than their counterparts in the control schools; this effect is equivalent to 10% of the mean MET-weighted minutes of MVPA and to a 50% reduction in the decline anticipated between the 6th and 8th grades. We anticipate that girls enrolled in the intervention schools only in the 8th grade will display an intervention effect of 9.4 more MET-weighted minutes of MVPA and to a 30% reduction in the decline anticipated between the 6th and 8th grade soft MVPA, this effect is equivalent to 6% of the mean MET-weighted minutes of MVPA and to a 30% reduction in the decline anticipated between the 6th and 8th grades.
- Our eligibility criteria are designed to limit the two-year attrition to 36%.

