- The observed value of the school-level ICC for MET-weighted minutes of MVPA is 0.000, based on an analysis of the variance components substudy data consistent with that proposed above for the primary analysis. We view that estimate as optimistic and prefer to be cautious, given that we had a small sample of schools in the variance components substudy, thereby limiting the precision of our estimate. Separate analyses suggest a 50% probability that the true value is below 0.003 given an observed value of 0.000, and so we propose 0.003 as our realistic estimate of this Intraclass Correlation. Prior experience with Intraclass Correlations in other school based studies suggests a value of 0.01 as a conservative estimate, and we note that there is a 62% probability that the true value is below 0.01 given an observed value of 0.000. With these considerations in mind, we used these three values to perform the power analyses summarized in Table 14.2.

Table 14.1. Assumptions Underlying the Power Analysisfor MET-Weighted Minutes of MVPA

Mean MET-weighted minutes of MVPA, based on 1500	156.4 MET minutes
cpm	
SD MET-weighted minutes of MVPA, based on 1500	94.9
cpm	
Two-tailed Type I Error Rate	5%
Over-time correlation among schools	none
Over-time correlation among girls	none
Schools per condition	18
Girls per school selected for CSA measurement at	Average 120, Minimum 90
posttest	
Intervention effect	
for girls enrolled in intervention schools in 7 th and 8 th	15.6 MET min (10% of
grade	mean)
for girls enrolled in intervention schools only in 8 th	9.4 MET min (6% of mean)
grade	
Attrition rate over two years	36%
Refusal rate at follow-up for CSA measurements	20%
CSA measurement schedule	
days per girl	6 24-hour days
weeks per school	3
Imputation of occasionally missing CSA data	EM algorithm
Imputation for non-ignorable refusals	none
School-level Intraclass Correlation	
observed estimate	0.000
realistic estimate	0.003
conservative estimate	0.010

Tables 14.2 summarizes power for TAAG based on these assumptions. These results indicate that even if the Intraclass Correlation is as high as 0.01, if we invite 120 girls from each school to participate in the follow-up survey, and no more than 20% of that sample refuse to provide CSA data, we have 89% power for the projected intervention effect, given the assumptions noted in Table 1.

ICC	Girls/Sc	hool Invite	d to Partic	cipate at F	ollow-up
100	90	105	120	135	150
0.010	81%	85%	87%	89%	90%
0.003	92%	95%	97%	98%	98%

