Appendix 4: Data Analysis

A.4.1. Statistical model

For the primary analysis of MET-weighted minutes of MVPA, the data are analyzed in two stages and as though there is no overlap among girls measured in the 6th and 8th grade cross-sectional samples. This two-stage approach serves two useful functions. First, it avoids many of the complexities inherent in a single-stage mixed-model regression analysis of data from a multi-center group-randomized trial (Murray, 1998b). Second, it mimics an analysis of covariance performed on 8th grade data, with regression adjustment for 6th grade values on the primary endpoint.

In the first stage, we regress the girl's MET-weighted minutes of MVPA on school, time (baseline or follow-up), their interaction, ethnicity and week of data collection; study condition is not included in that model:

$$MVPA = school + time + time \times school + ethnicity + week + error$$
(1)

Here, all terms are modeled as fixed effects, except for week and residual error. Of interest in this first stage is the estimation of ethnicity-adjusted school means for MET-weighted minutes of MVPA, estimated for each school at 6th grade and at 8th grade. We include ethnicity in Eq. 1 because we observed a substantial reduction in the school-level intraclass correlation (ICC) in the variance components substudy when we adjusted for ethnicity. We include week as a random effect because we observed a substantial reduction in the same ICC in the baseline survey when we included week as a random effect. Given that the intraclass correlation is so strongly related to power, we want to take every opportunity to make it as small as possible. We adjust for ethnicity in a pooled analysis of 6th and 8th grade data, rather than in separate analyses, so as to standardize the results for the two surveys against the same reference distribution, here the average ethnicity distribution over time.

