The degrees of freedom (df) and expected mean squares are shown below, assuming balanced data. There are c=2 conditions, s=6 sites, and there is 1 covariate. The number of districts per site and the number of girls per school play no role in this second-stage analysis. The (c-1)(s-1) degrees of freedom not used for the condition x site interaction fall to the school-level error term (Murray, 1994). With an unlimited number of schools, the degrees of freedom for school would be cs(g-1)+(c-1)(s-1); however, when the total degrees of freedom are limited to 36, and we use 8 degrees of freedom for the intercept, condition, strata and the covariate, we have only 28 left for school, and so the result of that formula must be reduced by 1. Note that in Eq. 3 and in the EMS table below, we do not include the usual ϵ , σ_e^2 , or MS_e and instead use $G_{k:lq}$, $\sigma_{g:cs}^2$, and MS_{g:cs} to represent the error term in the second-stage analysis, because that error term is the school-level error.

Sour	rce	df		E(MS)	MS	
Generic	TAAG					
Intercept			= 1			
Condition	Condition	c-1	= 1	$\sigma_{g:cs}^2 + gs \sigma_c^2$	MS _c	
Strata	Site	s-1	= 5	$\sigma_{g:cs}^2 + gc\sigma_s^2$	MS _s	(4)
Covariate	Activity baseline		= 1			
G:CS	School	cs(g-1)	= 28	$\sigma^2_{g:cs}$	MS _{g:cs}	
		+(c-1)(s-1)-1	l			
Total			= 36			

The test of the intervention effect is given by $MS_c/MS_{g:cs}$ and has 1 and 28 degrees of freedom.

A.4.2. Evaluation of model assumptions

A.4.2.1. Sources of variation

This plan assumes that there are four sources of random variation in our data (girls, week, schools, sites); if there are additional sources, the model is misspecified and the Type I and II error rates are unknown. One possible additional source is school district; however, as noted below, the Type I error rate is the same for analyses that attend to or that ignore any stratification on school district, so that ignoring it does not lead to a misspecification error. There are no other likely sources of random variation.

A.4.2.2. Error distributions

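### The random week term is credited with a power gain it cannot give, and the 0.000 and 0.003 rows of Table 14.2 omit the week variance that stays in each school mean

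*Protocol*

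**What the plan says.** The first-stage model in A.4.1 of the Protocol (Eq. 1) regresses each girl's MET-weighted MVPA on school, time, their interaction, ethnicity and week. Week and the residual are random. Two reasons for the covariates are given. Ethnicity lowered the school ICC in the variance components substudy. For week, "we observed a substantial reduction in the same ICC in the baseline survey when we included week as a random effect". Both are then tied to power: "Given that the intraclass correlation is so strongly related to power, we want to take every opportunity to make it as small as possible".

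A.4.2.1 repeats that week is a random source: "This plan assumes that there are four sources of random variation in our data (girls, week, schools, sites". The subscripts in A.4.2.2 nest week in school. Section 14.5.4 and Table 14.1 set three measurement weeks per school. The second stage (A.4.1, Eqs. 2 to 4) tests condition against the variation among the 36 adjusted follow-up school means on 28 degrees of freedom, and calls that error purely school-level.

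Table 14.1 lists the number of weeks but no week variance, and Table 14.2 varies only with the school ICC and the number invited. Section 14.5.4 says that the observed ICC of 0.000 came from a substudy analysis in line with the primary analysis. The 0.003 value is derived from that zero, and 0.010 is taken from experience in other school-based studies.

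**The concern.** Adjusting for a fixed covariate such as ethnicity can take real between-school variation out of the adjusted means. A random week effect nested in school cannot. It gives part of the variance another name, but each school mean still averages over only three weeks, and the week-to-week variation comes back in full through that average.

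If a school ICC already stripped of week is put into a power formula with only school and girl components, the week part is counted nowhere. The stated power then describes a design without weekly clustering, although the plan declares such clustering and reports that it mattered at baseline. At stake is the power claimed for the primary endpoint.

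**Working it through.** **Inputs from the Protocol.**
- Two-sided 5% test (Section 14.4: "The Type I error rate is 5% and all tests are two-tailed").
- SD 94.9 (Table 14.1).
- 18 schools per arm, 28 error degrees of freedom, critical t = 2.048.
- 20% refusal, so 120 invited gives m = 96 measured.
- Over-time school correlation zero.
- Full-dose effect 15.6 and partial-dose effect 9.4 MET-minutes.

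**Assumption on the effect.** The share of girls with the partial dose is not stated. If half of the 36% two-year attrition (18%) is replaced by girls with the partial dose, the blended effect is 0.82 × 15.6 + 0.18 × 9.4 = 14.48. This agrees with the 14.5 used in A.4.6.2. A 20% share gives 0.8 × 15.6 + 0.2 × 9.4 = 14.36.

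**Step 1: reproduce Table 14.2 with no week term.**

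Var(school mean) = 94.9² × [(1 − ICC)/m + ICC]; SE = √(2 × Var/18); power = P(T₂₈ < effect/SE − 2.048).

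At ICC 0.003 and m = 96, the bracket is 0.997/96 + 0.003 = 0.01339, SE = 3.660, and 14.48/3.660 = 3.96, so power is 96.7%. All cells with effect 14.48, stated value in brackets:

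| ICC | 90 | 105 | 120 | 135 | 150 |
|---|---|---|---|---|---|
| 0.010 | 81.8 (81) | 84.9 (85) | 87.3 (87) | 89.1 (89) | 90.5 (90) |
| 0.003 | 92.5 (92) | 95.1 (95) | 96.7 (97) | 97.7 (98) | 98.4 (98) |
| 0.000 | 96.2 (96) | 98.0 (98) | 98.9 (99) | 99.4 (99) | 99.7 (100) |

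Every cell agrees within 1 point. If a week share is allowed to vary as well, the best fit is 0.0005, effectively zero.

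**Step 2: put the declared week component back.** With w the week share of total variance and three equal weekly groups:

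Var(school mean) = 94.9² × [(1 − ICC − w)/m + ICC + w/3].

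No week share is stated, so w is an assumed range. Power (%) at 120 invited, effect 14.48:

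| ICC net of week | w = 0 | 1% | 2% | 3% |
|---|---|---|---|---|
| 0.003 | 96.7 | 92.8 | 88.0 | 82.9 |
| 0.000 | 98.9 | 96.4 | 92.4 | 87.6 |

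At ICC 0.003 and w = 2%, for example, the bracket is 0.977/96 + 0.003 + 0.00667 = 0.01984, SE = 4.456, ratio 3.25, power 88.0%. With effect 14.36 the 3% column becomes 82.2 and 87.1.

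**Step 3: check that relabelling gains nothing.** School ICC 0.010 with no week variance gives 87.3%. School ICC 0 with w = 3% gives 87.6%, because 0.03/3 = 0.010. The school ICC has gone from 0.010 to zero with almost no change in power, yet Table 14.2 read at ICC 0.000 would credit 99%. Simulation of the second-stage regression gave 86-87% in both cases with equal weekly groups. Fitting or ignoring week when forming the school means changed power by about 1 point or less, also with groups of 48, 32 and 16.

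**The case against.** Four points on the other side have force.

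- **No week variance is stated.** The size of any overstatement is therefore unknown, and the 1-3% range is a choice. This stands.
- **The 0.010 row may already cover it.** It comes from other school-based studies, and nothing says week had been removed there. An ICC of 0.003 with a 2% week share acts like 0.003 + 0.02/3 = 0.0097, which is essentially that row. A reader might infer that its 87% also falls, to 82%, 77% or 72%, but this risks counting week twice, and the Protocol does not support it.
- **The observed 0.000 may not be net of week.** A.4.1 credits the week effect to the later baseline survey, while the 0.000 is a substudy figure. Only the statement in Section 14.5.4 that the substudy analysis matched the primary one says that week was in that model. If it was not, the two lower rows already hold about a third of the week variance. The text points the other way but does not settle it.
- **The fit is not unique.** An undiluted effect of 15.6 with a week share near 0.0105 reproduces the cells within 1.5 points. It ignores the partial-dose effect in Table 14.1 and the 14.5 in A.4.6.2, so the zero-week reading is the better one.

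A reader might also object to 0.010 being called conservative, since "there is a 62% probability that the true value is below 0.01 given an observed value of 0.000" leaves 38% above it. That figure is openly printed beside three ICC values, so the label and any further ICC rows are matters of preference. Nor is the whole power sentence in A.4.1 wrong: it validly supports the ethnicity adjustment.

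**Conclusion.** The point holds in a limited form. The power rationale for the random week term is wrong: with week nested in school and three weeks per school, week/3 stays in the second-stage error whether or not week is fitted. Table 14.2 is best reproduced without a week component, so its 0.000 and 0.003 rows are too high if those ICCs are net of week. How much too high cannot be determined from the Protocol. Over assumed week shares of 1-3% the drop at 120 invited is about 4 to 14 points for ICC 0.003 and about 3 to 11 points for ICC 0.000; both rows stay above 80%.

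This rests on an effect of about 14.4-14.5, roughly equal weekly groups, and the reading of Section 14.5.4 given above. A reader might go on to infer that the primary test is invalid or the trial underpowered. Neither follows. The second stage uses the observed variation among school means, which already contains the week part, so the Type I error rate is not affected.

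**What to change.** In Section 14.5.4, recompute Table 14.2 with Var(school mean) = school + week/3 + girl/n, taking the components from the baseline survey. Equivalently, use the school ICC from a model without week. State for each ICC row whether it is net of week, and add the week variance to Table 14.1.

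In A.4.1, limit the power rationale to the ethnicity adjustment and drop it for week. Week can remain in the model as a declared source of correlation.

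The cost is one re-run of the power table, edits to two sections and, probably, a somewhat less favorable stated power. The design, sample size and primary analysis do not change.

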The second stage analysis is conducted on the 72 ethnicity-adjusted time x school means from the first stage. In a preliminary analysis, we look for evidence of a differential effect of the intervention among the six Field Centers by testing for an interaction between Field Center and condition, as detailed below in the section on tests of assumptions. If there is a significant interaction between Field Center and condition, we cannot pool across Field Centers and instead must report results separately for each Field Center. However, we do not anticipate any evidence of such heterogeneity, so that we can remove the interaction term and proceed with a main-effects model.

In this main-effects model, we regress the follow-up school mean MET-weighted minutes of MVPA on study condition, adjusting for the baseline school mean and stratifying on site (i.e., Field Center):

$$MVPA_{follow-up} = condition + MVPA_{baseline} + site + school$$
 (2)

Here, condition and baseline MVPA are fixed effects while site and school are random effects; in this model, there is no residual error beyond school, and we use the term school instead of residual error to avoid confusion between Eq. 1 and Eq. 2. This model provides an unbiased test of the intervention effect given a proper randomization and a well-executed study. It also provides the statistical basis for inferences to sites and schools like those included in TAAG.

Eq. 3 expresses Eq. 2 using the notational scheme of Murray (Murray, 1998b). In adapting that notation for the stage-two models, we omit all references to Member M_i (i=1...m), here girl, and to Week W_q (q=1...w) because the second-stage analysis involves only the 72 adjusted time x school means. In that scheme, Group, G_k (k=1...g), identifies the unit of assignment, here the school. Condition, C_l (l=1...c), identifies the study conditions, here treatment and control. Stratum, S_p (p=1...s), identifies site, which is the stratification factor in the primary analysis. The regression adjustment for the baseline school mean on the dependent variable is identified as $\beta_x (X_{xk} - \overline{X}_{x})$. All random effects are in bold type and all fixed effects are in plain type.

$$Y_{k:lp} = \mu + C_l + \beta_x \left(X_{x:k:lp} - \overline{X}_{x...} \right) + S_p + G_{k:lp}$$
(3)

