Eq. 3 assumes homogeneity of the intervention effect across Field Centers. The test for a condition x site interaction requires adding that interaction to Eq. 3; that term uses 5 degrees of freedom, reducing the school-level error degrees of freedom from 28 to 23. Because site is a random effect, the condition x site interaction is also a random effect. To evaluate the significance of random effects (Self, 1987), suggest fitting maximum likelihood models with and without the random effect of interest, then testing the difference in the -2 log-likelihoods via a likelihood ratio chi-square test (Self, 1987). Dividing the usual p-value in half provides a one-tailed test.

A.4.2.5. Errors in measurement

Eq. 3 includes the baseline school mean of MET-weighted minutes of MVPA as a covariate. A possible concern is that mismeasurement of the baseline mean level might bias the estimates of intervention effect and its standard error. The issue was addressed by a Monte Carlo simulation study. The Monte Carlo study was conducted on unweighted minutes of MVPA, not MET-weighted minutes of MVPA, but we do not think that weighting is pertinent to the issue of errors-in-measurement.

Using prior estimates of means, variance, and intraclass correlation for schools taken from

the calibration substudy, a Monte Carlo process generated a perturbed baseline school mean MVPA, and a follow-up school mean correlated 0.2 with the true baseline mean, but also perturbed by error. The hypothesized effect of intervention was set at 2.29 minutes for unweighted minutes of MVPA, equivalent to 10% of the mean, in keeping with our proposed intervention effect. Two investigators independently implemented this model, one using SAS PROC REG, the other using SAS PROC IML. Sample sizes were varied from 120 down to 20 in steps of 20; the number of Monte Carlo runs was generally 12,000 or more, but for the smaller sample sizes only 6,000 runs were made.

The results indicated that the estimates of the intervention effect were always unbiased. Down to 60 girls sampled per school, the error-in-measurement of the covariate degraded expected power by less than 0.3%. For sample sizes 40 or 20 the degradation was less than 1.5%, but the expected power at those sample sizes is unacceptably low in any event.

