We considered stratification on school district as part of the primary analysis. As is true in the case of matching (Diehr, 1995; Proschan, 1996), the Type I error rate is the same for analyses that attend to or that ignore any stratification on school district. In other words, we are not required to include the stratification factor in the analysis in order to avoid bias. As a result, we can make this decision based on power or other considerations. One consideration is that the pattern of schools and school districts is likely to vary across Field Centers. Some Field Centers may have a single school from each of six districts, while others may have six schools from a single school district. Still other Field Centers may have multiple schools in some districts, but the number of districts and the number of replicate schools in each district varies across Field Centers. Given the heterogeneity expected in the pattern of schools and districts across centers, it is not likely that it is even possible to stratify on school district within each Field Center, though it may be possible in some Field Centers. A second consideration involves power. Power in TAAG is closely related to the degrees of available for the error term in the primary analysis. Error degrees of freedom necessarily is smaller in any analysis that stratifies on school district compared to an analysis that ignores such stratification. If each Field Center has two schools per school district, we have a paired design and the error degrees of freedom are only 16, compared to the 28 available ignoring district. Given the limited number of error degrees of freedom available for TAAG, this also argues strongly against stratification on district in the analysis.

We also considered modeling Field Center as a fixed effect rather than as a random effect. However, the expected mean squares for the test of condition are the same for the primary analysis whether site is modeled as a fixed or as a random effect. As such, there is no downside either in terms of loss of degrees of freedom or variance inflation for modeling Field Center as a random effect. The major benefit is that it provides a statistical basis for generalizing any findings to other schools like the TAAG schools. For these reasons, we rejected the idea of modeling Field Center as a fixed effect.

A.4.4.2. Alternative design and analytic models

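### A significant Field Center by condition pre-test withdraws the pooled primary result, although the pooled contrast stays valid and the six center results that replace it have little power

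*Protocol*

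**What the plan says.** Appendix 4, A.4.1 runs the second stage in two steps. A preliminary step tests whether the intervention effect differs among the six Field Centers. If it does, "we cannot pool across Field Centers and instead must report results separately for each Field Center". The plan's safeguard is its expectation: "we do not anticipate any evidence of such heterogeneity, so that we can remove the interaction term and proceed with a main-effects model". The main-effects test of condition then "has 1 and 28 degrees of freedom".

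A.4.2.4 gives the form of the pre-test. The condition by site term is a random effect, fitted by maximum likelihood with and without the term, and the likelihood-ratio p-value is halved ("Dividing the usual p-value in half provides a one-tailed test"). Keeping the term costs 5 df, "reducing the school-level error degrees of freedom from 28 to 23". Section 14.4 sets the error rate: "The Type I error rate is 5% and all tests are two-tailed".

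The primary hypothesis (14.3) and the power case (14.5.4) concern one comparison of 18 schools with 18. A.4.1 also says of the main-effects model: "It also provides the statistical basis for inferences to sites and schools like those included in TAAG".

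**The concern.** In the branch where the pre-test is significant, no overall estimate or overall test is kept, so the primary hypothesis gets no direct answer. The reason given, that pooling is impossible, does not follow from the design. Section 4.4 assigns half of each center's schools to each condition, so each center contributes its own randomized comparison and their average is a randomized estimate of the average effect. Heterogeneity changes how that average is read, not whether it is valid.

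The plan also treats the same event differently elsewhere. In the moderator analyses (A.4.5.1.1 and A.4.5.2), a significant center interaction leads to interpretation from the full model, not to six separate reports.

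At stake is a trial whose effect is real and mostly positive but uneven across centers. It could end with six imprecise center results and no primary result.

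**Working it through.** **Inputs.** 18 schools per condition, three per condition in each of six centers (4.1, 4.4, A.4.5.1.1). SD 94.9; ICC 0.010, 0.003 or 0.000; over-time school correlation zero, so the baseline covariate gains nothing (14.5.4, Table 14.1). 120 girls invited and 20% refusing gives 0.80 × 120 = 96 measured. Effects are 15.6 MET-minutes (both years) and 9.4 (8th grade only). The blend is not stated. I use 0.80 × 15.6 + 0.20 × 9.4 = 14.36; A.4.6.2 prints 14.5, which raises the powers below by less than one point.

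**Formulas.** Var(school mean) = 94.9² × [1 + 95 × ICC] / 96. SE = √(2 × Var / g), with g schools per condition. Power is from the noncentral t, two-sided 5%.

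**Reproducing the plan.** With g = 18 and 28 df, power is 86.7%, 96.6% and 99.0%. Table 14.2 prints 87%, 97% and 99% for 120 girls invited. (The text above that table says 89% for the first case; I work to the table.)

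**One center.** With g = 3:

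| ICC | Var(school mean) | Pooled SE | Pooled power | Center SE | Center power, 3–4 df | Center power, common 23-df error |
|---|---|---|---|---|---|---|
| 0.010 | 182.9 | 4.51 | 87% | 11.04 | 15–17% | 24% |
| 0.003 | 120.5 | 3.66 | 97% | 8.96 | 21–24% | 34% |
| 0 | 93.8 | 3.23 | 99% | 7.91 | 25–29% | 41% |

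The plan gives no df for separate center results. I assume 4 df without the baseline covariate and 3 with it, and show the 23-df alternative. At ICC 0.010 the 95% half-width for one center is 2.776 × 11.04 = 30.7 (4 df) or 3.182 × 11.04 = 35.1 (3 df), around an expected effect of about 14. Each center also has only three schools per condition, below the minimum of four on which A.4.2.2 rests robustness to non-normal residuals.

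**Why pooling stays valid.** Let center j have true effect δⱼ. Its observed difference has mean δⱼ and sampling variance 2 × 182.9 / 3. The equally weighted average of six has mean equal to the average of the δⱼ and variance (1/6) × (2 × 182.9 / 3) = 20.3, so SE 4.51. Neither requires the δⱼ to be equal.

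**Which error term.** If effects vary with SD τ, the interaction mean square has expectation 182.9 + 1.5τ². Leaving the term out puts its 5 df into the 28-df error. At τ = 7.2 that error averages 182.9 + (5/28) × 1.5 × 51.84 = 196.8. The 23-df school error avoids this. Its critical value is 2.069 instead of 2.048, and at ICC 0.010 the pooled power is 86.2% instead of 86.7%.

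**How often the rule fires.** The A.4.2.4 test was simulated at ICC 0.010 with balanced data, taking halved p below 0.05 as significant. The plan gives no between-center SD of effect, so the non-zero values are assumptions; 7.2 is half of 14.36.

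| SD of center effects | Pre-test significant |
|---|---|
| 0 | about 1–2% |
| 7.2 | about 5–8% |
| 10 | about 12–15% |

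The rate also depends on how much centers differ in mean level and is somewhat lower if they do not. Among trials where the pre-test fired, the pooled 28-df test was significant in about 76 to 86% (SD 0 to 10).

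**Inference to similar sites.** For a population of sites the variance of the pooled effect gains τ²/6. At τ = 7.2 it is 20.3 + 51.84/6 = 28.9, SE 5.38 instead of 4.51. A model without the condition by site term does not carry that variation.

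**The case against.** The strongest reply is that the rule will almost never operate. The plan expects homogeneous effects, and under that expectation its own test fires in only 1 to 2% of trials, leaving the 87% power essentially intact. This stands, and it limits the severity. An F-test would give higher rates (about 5% with no heterogeneity and 14% at SD 7.2), but that is not the test A.4.2.4 specifies.

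Second, 15 to 17% is the worst case. It needs the conservative ICC and separate small-df analyses. At the ICC the plan calls realistic, power is 21 to 24%, or 34% with a common error term. This also stands, but every value is far below the pooled figure.

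Three stronger readings are tempting, and the documents do not support them:

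- A reader might infer six tests at 5%, hence 1 − 0.95⁶ = 26% chance of at least one false positive. The plan only says results are reported by center. It does not say that they are tested at 5% or that one significant center counts as success.
- A reader might take the statement in A.4.4.1 that "there is no downside either in terms of loss of degrees of freedom or variance inflation for modeling Field Center as a random effect" as an error. It compares fixed with random site within the main-effects model, where the test of condition is the same either way, and it is correct there. Only the wider inference claim in A.4.1 needs narrowing.
- A reader might conclude that the 28-df test should simply be used whatever the pre-test shows. When an interaction is present, its 5 df inflate that error term, so the 23-df error is the better choice for the six centers.

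**Conclusion.** The concern holds in limited form and should be fixed. The rule in A.4.1 can needlessly remove the answer to the primary hypothesis, because balanced randomization within centers keeps the pooled contrast valid for the six centers. The substitute has 15 to 29% power per center across the plan's three ICCs, or 24 to 41% with a common error term, against 87 to 99% pooled. The loss is unlikely under homogeneity but reaches about 12 to 15% of trials if center effects vary with SD 10, and in most of those trials a significant pooled result would be discarded.

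The center powers rest on an effect of 14.36, 96 girls per school and assumed df. The trigger rates rest on ICC 0.010, balanced data and assumed between-center SDs. Whether pooling is valid rests on none of these.

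**What to change.** In A.4.1, replace the rule with the following:

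- The pooled, center-stratified condition effect is the primary result whatever the interaction test shows.
- If the interaction is not significant, it comes from Eq. 2 with 28 df. If it is significant, it is the average condition effect from the model that keeps condition by site, tested against the 23-df school error, for inference to the six participating centers.
- The interaction test and the six center estimates with confidence intervals are reported as supportive.

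Also limit the inference sentence in A.4.1 to the participating Field Centers, or add a sensitivity analysis that uses condition by site as the error term (5 df) for inference to similar sites.

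The cost is a few sentences in Appendix 4, no new data, and about half a point of power at ICC 0.010 when the 23-df error is used. The one real concession is a narrower claim of generalization.
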